3.2 Inclusion Criteria

1. Subject is, in the investigator's opinion, willing and able to comply with the protocol requirements.
2. Subject has given voluntary written informed consent before performance of any study-related procedure not part of normal medical care, with the understanding that consent may be withdrawn by the subject at any time without prejudice to their future medical care.
3. Must have received 2 consecutive cycles of systemic myeloma therapy.
4. Documented refractory or relapsed and refractory (R/R) multiple myeloma
 - a. patients had less than minimal response, or had achieved at least a minimal response to previous treatment, but progressed within 6 months
 - b. patients who have failed treatment with, are intolerant to, or are not candidates for all available therapies known to be active for treatment of relapsed or refractory myeloma
 - c. patients must have failed, be intolerant or are ineligible to treatment with at least 3 lines of therapy, including an IMiD, proteasome inhibitor and anti-CD38 agent
5. Targetable plasmacytoma, either intra-or extramedullary that is visualized on imaging (PET/CT or MRI) and is causing symptoms (eg. pain, neurological compromise) or potential to cause symptom as per clinician's judgement; and measurable disease at screening, defined as one or more of the following:
 - a. Serum IgG, IgA, or IgM M-protein ≥ 0.5 g/dL
 - b. Urine M-Protein ≥ 200 mg excreted in a 24-hour collection sample
 - c. Involved serum free light chain (sFLC) > 100 mg/L provided the FLC ratio is abnormal
6. Males and Females at least 18 years or legal age of consent per local regulations.
7. Women of childbearing potential (WOCBP) must have two negative serum or urine pregnancy tests (minimum sensitivity 25 mIU/mL or equivalent units of HCG). One 10-14 days prior to start of the study drug and one within 24 hours prior to the start of study drug.
8. Investigators shall counsel WOCBP and male subjects who are sexually active with WOCBP on the importance of pregnancy prevention and the implications of an unexpected pregnancy. Investigators shall advise WOCBP and male subjects who are sexually active with WOCBP on the use of highly effective methods of contraception. Highly effective methods of contraception have a failure rate of < 1% when used consistently and correctly.
9. No condition which would cause unacceptable risk.

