5.1 Schedule of Assessment

Procedure	Screening (Day 0)	C1D1 (±3 days)	C1D15 (±3 days)	Cycles 2-4		Cycles 5+	Cycles 5+	End of Study
				D1	D15	D1	D15	
Informed Consent	X							
Medical History	X	X		X		X	X	X
Physical Exam	X	X		X		X	X	X
Vital Signs + weight	X	X	X	X	X	X	X	X
Performance Status (ECOG)	X	X		X		X	X	X
Concomitant Medications	X	X	X	X	X	X	X	X
Second Primary Malignancy	X	X	X	X	X	X	X	X
Adverse Events Assessment	X	X	X	X	X	X	X	X
Bone Marrow Aspiration/Biopsy ^a	X ^a			X ^a		X ^a		X ^a
Biopsy of Targeted Lesion	X							
Radiologic bone imaging:								
PET/CT, MRI	X				X			X
CBC w/ plts & diff	X	X	X	X	X	X	X	X
CMP, Mg, Uric Acid, LDH	X	X	X	X	X	X	X	X
Serum or urine pregnancy test	X	X	X	X	X	X	X	X
TSH	X			X		X		
Beta 2 microglobulin	X			X				
Response Assessment								
Serum quantitative immunoglobulins	X	X		X		X		X
free light chains, SPEP & SIFE	X	X		X		X		X
24-Hour urine for urine total protein	X	X		X		X		X
UPEP & UIFE	X	X		X		X		X
TREATMENT								
Nivolumab Infusion ^c		X ^c	X ^c	X ^c	X ^c	X ^c	X ^c	
Radiation to Targeted Lesion ^b		X ^b						
RESEARCH PROCEDURES								
Stool Samples (before nivo infusion) ^d		X ^d			X ^d	X ^d		
Saliva Sample collection (before nivo)		X						

Foot notes:

- a. Bone marrow aspirate pre-nivolumab infusion on C2D1, C4D1, C7D1, C10D1 and Q 12 weeks thereafter and as needed to confirm CR
- b. One course of radiation (6GY x 5 fractions), with first radiation on D1 AFTER IV nivolumab
- c. All Infusions will have a ± 3 day window.
- d. Stool samples will be collected on Day1, end of Radiation, C4D1 and C7D1.

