5.1.2 Treatment Phase

Once eligible, patients will receive immunotherapy, nivolumab, intravenously at 240 mg every two weeks. Infusions will be given over 30 minutes (not bolus or IV push). Patients will also receive radiation of 6 Gy x 5 fractions the first week of starting immunotherapy. Immunotherapy treatment starts with the first radiotherapy fraction. Nivolumab will be given every 2 weeks. Patients will have specified laboratory values measured monthly and evaluated for response as defined by International Myeloma Working Group Criteria. Patients will continue to receive their respective immunotherapy for up to three years or until disease progression or dose limiting toxicity is reached. Patients will remain on therapy for up to 6 cycles in the setting of stable disease and for up to a year in the setting of a PR or better by 6 cycles.

5.2 Response Assessment at Week 12

Patients will have specified laboratory values measured monthly and evaluated for response as defined by International Myeloma Working Group Criteria. Patients without progression of disease as defined by IMWG criteria including assessment of plasmacytoma(s) by PET/CT will continue to receive nivolumab every 2 weeks.

5.3 Duration of Therapy and Criteria for Removal from Study:

In the absence of treatment delays due to adverse event(s), treatment may continue until one of the following criteria applies:

1. Progression of disease as defined by IMWG criteria,
2. Intercurrent illness that prevents further administration of treatment,
3. Unacceptable adverse event(s),
4. Patient decides to withdraw from the study, or
5. General or specific changes in the patient's condition render the patient unacceptable for further treatment in the judgment of the investigator.

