9.1 Standard IMWG Response Criteria

Response to multiple myeloma will be assessed based on the International Myeloma Working Group Criteria (IMWG) as described in the table below.

Standard IMWG response criteria*	
Stringent complete response	Complete response as defined below plus normal FLC ratio** and absence of clonal cells in bone marrow biopsy by immunohistochemistry (κ/λ ratio $\leq 4:1$ or $\geq 1:2$ for κ and λ patients, respectively, after counting ≥ 100 plasma cells)++
Complete response	Negative immunofixation on the serum and urine and disappearance of any soft tissue plasmacytomas and $< 5\%$ plasma cells in bone marrow aspirates
Very good partial response	Serum and urine M-protein detectable by immunofixation but not on electrophoresis or $\geq 90\%$ reduction in serum M-protein plus urine M-protein level $< 100\text{mg per 24 hours}$.
Partial response	$\geq 50\%$ reduction of serum M-protein plus reduction in 24 h urinary M-protein by $\geq 90\%$ or to $< 200\text{ mg per 24h}$; If the serum and urine M-protein are unmeasurable, a $\geq 50\%$ decrease in the difference between involved and unininvolved FLC levels is required in place of the M-protein criteria; If serum and urine M-protein are unmeasurable, and serum-free light assay is also unmeasurable, $\geq 50\%$ reduction in plasma cells is required in place of M-protein, provided baseline bone marrow plasma-cell percentage was $\geq 30\%$. In addition to these criteria, if present at baseline, a $\geq 50\%$ reduction in the size (SPD)§§ of soft tissue plasmacytomas is also required.
Minimal response	$\geq 25\%$ but $\leq 49\%$ reduction of serum M-protein and reduction in 24-h urine M-protein by 50–89%. In addition to the above listed criteria, if present at baseline, a $\geq 50\%$ reduction in the size (SPD)§§ of soft tissue plasmacytomas is also required.

Stable disease	Not recommended for use as an indicator of response; stability of disease is best described by providing the time-to-progression estimates. Not meeting criteria for complete response, very good partial response, partial response, minimal response, or progressive disease

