10.2 Regulatory Considerations

All protocol amendments and consent form modifications will be made by the Principal Investigator. *Bristol-Myers Squibb* will have the opportunity to review and approve the changes prior to submission of these changes to the local IRB.

11 Statistical Considerations

The primary endpoint of this study is response rate. The trial design is a single arm, single-center, Simon optimal two-stage design. Patients will be evaluated for response at 12 weeks (84 days \pm 7 days). Patients will be enrolled in two stages with 13 patients in the first stage, and potentially an additional 13 patients in the second stage. The decision to enroll patients into the second stage will depend on the number of responses observed in the first stage, as described below.

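### As printed, the calendar puts no PET/CT or MRI inside the week-12 response window (days 77-91), so a plasmacytoma response or new lesion arising after about day 71 goes unseen at the primary assessment

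*Combined protocol and SAP*

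**What the plan says.** - **Time point.** Section 11: "Patients will be evaluated for response at 12 weeks", with a tolerance of 7 days either side of day 84.
- **Endpoint.** Section 1.1 defines systemic response as a best response of partial or complete within that period, not as status on day 84 alone.
- **Imaging in the text.** Under the week-12 heading, section 5.2 says: "Patients without progression of disease as defined by IMWG criteria including assessment of plasmacytoma(s) by PET/CT will continue to receive nivolumab every 2 weeks".
- **Imaging in the calendar.** In section 5.1 the PET/CT, MRI line under "Radiologic bone imaging" is marked at Screening, in the D15 column of cycles 2-4, and at End of Study. No footnote says which of cycles 2-4 is meant.
- **Role of imaging in response.** In the section 9.1 table, the partial response row adds: "In addition to these criteria, if present at baseline, a" reduction of at least 50% in the SPD of soft tissue plasmacytomas is needed. Complete response needs such lesions to disappear. A footnote to the same table says radiographic studies are not needed to satisfy the response categories.
- **Population.** Inclusion criterion 5 requires a "Targetable plasmacytoma, either intra-or extramedullary that is visualized on imaging (PET/CT or MRI"), so every patient has an imaged lesion, which may be intramedullary.

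**The concern.** For a patient with a soft tissue plasmacytoma at baseline, a partial or complete response has two parts: the M-protein or light-chain criterion and the lesion measurement. The plan collects the first inside the week-12 window, at C4D1, and the second about two weeks before and two weeks after. No rule says which scan goes with the day-85 laboratory values. A lesion that first shrinks enough after day 71 has no scan to show it by the time of assessment. A new lesion arising after day 71, which would count as progression, is not seen either. The day-99 scan would show both, but the plan does not say whether it may be used. Different assessors could therefore classify the same patient differently, under a decision rule in which one patient can stop the trial or change its conclusion.

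**Working it through.** **Inputs**
- Window: 84 ± 7 days (section 11), so days 77 to 91.
- Cycle length: not stated. Section 5.1.2 says "Nivolumab will be given every 2 weeks" and the calendar has D1 and D15 columns, giving 2 × 14 = 28 days. The marrow footnote (C4D1, C7D1, C10D1, then every 12 weeks) fits: 3 cycles × 28 = 84 days.
- Visit tolerance: "All Infusions will have a ± 3 day window". This is stated for infusions and the cycle 1 columns; applying it to scans is an assumption.

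**Step 1: visit days.** Study day = 28 × (cycle − 1) + day in cycle, with the first dose as day 1.

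| Visit | Day | With ± 3 days | In 77-91? | Imaging mark? |
|---|---|---|---|---|
| C2D15 | 28 × 1 + 15 = 43 | 40-46 | no | yes |
| C3D15 | 28 × 2 + 15 = 71 | 68-74 | no | yes |
| C4D1 | 28 × 3 + 1 = 85 | 82-88 | yes | no |
| C4D15 | 28 × 3 + 15 = 99 | 96-102 | no | yes |

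The day-71 scan is 77 − 71 = 6 days before the window opens; the day-99 scan is 99 − 91 = 8 days after it closes. A 3-day tolerance bridges neither gap. Counting the first dose as day 0 gives 42, 70 and 98, with the same result. C4D1 carries the serum and urine response tests and the marrow. The nearest scans are 85 − 71 = 14 days earlier and 99 − 85 = 14 days later.

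**Step 2: what the earlier scans can do.** Days 43 and 71 both precede day 84, so under section 1.1 they can document a lesion response reached by then. The uncovered stretch runs from day 71 to the week-12 assessment.

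**Step 3: sensitivity of the decision rule.** First the plan's own figures. The trial stops if there are 3 or fewer responses in 13 and succeeds if there are 10 or more in 26:

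P(success) = Σ over x = 4 to 13 of P(X₁ = x) × P(X₂ ≥ 10 − x), with X₁ and X₂ independent Binomial(13, p).

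At p = 0.20 this is 0.021 (plan: 0.025, so within its limit). At p = 0.40 it is 0.606 (plan: 60%).

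Now suppose a share of true responders cannot be counted for want of a timely scan. The documents give no such share; the range is an assumption.

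| Share of responders lost | Countable rate | P(success) | P(stop at stage 1) |
|---|---|---|---|
| 0% | 0.40 | 0.606 | 0.169 |
| 5% | 0.40 × 0.95 = 0.38 | 0.525 | 0.208 |
| 10% | 0.40 × 0.90 = 0.36 | 0.443 | 0.254 |
| 20% | 0.40 × 0.80 = 0.32 | 0.283 | 0.360 |

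These figures show how steep the rule is. They do not estimate the loss.

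**The case against.** A reader might infer that the primary endpoint has no imaging component at all, or that every patient's response is unverifiable. The documents do not support that, for four reasons.

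1. Section 1.1 counts best response within 12 weeks, so the day-43 and day-71 scans can supply the lesion criterion. This stands, and it confines the gap to the period after day 71.
2. Section 5.2 itself names PET/CT at week 12. The problem is a mismatch between text and calendar rather than a failure to plan imaging. The sentence also concerns who continues treatment, not how the endpoint is scored. Both points stand, and they are why the sections need reconciling.
3. The SPD and disappearance rules cover soft tissue plasmacytomas. Patients whose only lesions are intramedullary may be unaffected, and the plan does not say how many there will be. This stands.
4. The section 9.1 footnote says radiographic studies are not needed. It sits against the partial and complete response rows of the same table and against section 5.2. It neither removes the problem nor can be ignored; the conflict has to be settled.

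The most serious objection is that the point rests on one column position. In the same column the stool mark sits under D15, although its own footnote says C4D1. The marrow marks do agree with their footnote, so a general shift is not shown, but one misplaced mark cannot be excluded. If the imaging mark belongs under D1, the C4D1 scan falls on day 85 and the gap closes, provided cycle 4 is meant. A mark over grouped cycles also need not mean every cycle: the marrow row is marked across cycles 2-4, yet its footnote names only C2D1 and C4D1. With no imaging footnote, clarification is needed on either reading.

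Sections 6.2 and 6.4 mention response assessment every 2 weeks, but neither names imaging there.

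**Conclusion.** The point holds in limited form. As printed, and with 28-day cycles inferred, no scan falls within days 77-91, although section 5.2 names PET/CT under the week-12 heading. Lesion responses first reached after day 71, and new lesions between day 71 and the assessment, are missed. The status of a day-99 scan is undefined.

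The effect on the response rate is unknown. It depends on how many patients have soft tissue plasmacytomas and how many of those change status late. It could still matter, because decisions turn on one patient (3 versus 4 of 13; 9 versus 10 of 26) and power at a 40% response rate is only about 60%.

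A reader might also infer an inflated false-success rate from counting day-99 shrinkage. The wording of section 1.1, which limits response to the 12-week period, weighs against counting it, so that should not be claimed as a consequence of the plan.

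This should be fixed, with moderate confidence because of the column-position question.

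**What to change.** 1. Check the imaging mark against the source calendar, and add a footnote naming the cycles and days on which scans are due.
2. Place the cycle-4 scan at study day 84 ± 7, alongside the C4D1 laboratory tests and marrow, moving it from C4D15.
3. Keep the cycle 2 and 3 scans. They support earlier best responses and the detection of progression for PFS.
4. State in sections 9.1 and 11 that the week-12 scan, together with earlier scans for best response, supplies the plasmacytoma component of the primary endpoint, and that scans after day 91 do not count towards it.
5. Reconcile sections 5.1, 5.2, 9.1 and 11, including the footnote on radiographic studies, and say how patients with only intramedullary lesions are handled.

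Cost: a calendar amendment and a few sentences, with no added scan. The downside is that cycle-4 imaging comes about two weeks earlier (day 99 to about day 85).

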5.4 Duration of Follow Up

Patients will be followed for 3 years after removal from study or until death, whichever occurs first. Patients removed from treatment for unacceptable adverse events will be followed until resolution or stabilization of the adverse event

6 Radiation Therapy Guidelines

6.1 Planning

After informed consent is obtained, a targetable plasmacytoma lesion that is accessible for biopsy is selected by the treating physician as the site for local radiotherapy under Standard of Care practices to establish a diagnosis. The area of interest is imaged at CT planning for conformal treatment. There is no contrast media used in the CT planning. There is an exposure to small amounts of radiation with the use of CT scan. CT scan thickness should be ≤ 0.5 cm through the tumor region. These images will be used in 3D treatment planning in accordance with the dose specification constraints.

The CTV is defined as the plasmacytoma lesion of interest with the expected motion changes, while the PTV is the CTV plus a margin ≤ 1 cm, dependent on the anatomical location, to account for setup uncertainty. While gating is not part of the current conformal setting at Stich Radiation Center, WCM, efforts are made to consistently treat chest and abdominal lesions with the patient maintaining shallow breathing, to limit the movement of the volume treated during respiration.

6.2 Treatment

Radiotherapy is delivered by external beam using linear accelerators capable of delivering ≥ 4 megavoltage x-rays. The PTV will encompass all of the biopsied plasmacytoma lesion, and will be defined by the treating physician. The PTV will be treated daily, Monday-Friday. A dose of 30 Gy in 5 fractions of 6 Gy each is delivered, daily, to an isodose surface encompassing $\geq 90\%$ of the PTV.

Radiation Dose specification: The planning target volume receives a minimum of 90% of the prescription dose.

Treatment Machine: A linear accelerator with ≥ 4 MV x-rays is required.

Immobilization Technique: Patients will be set-up for treatment and CT scanning, and planned for treatment. The specific immobilization technique will be determined at the discretion of the treating physician.

Target Positioning Verification: Digitally acquired radiographic images will be used to verify the position of the target with respect to the treatment machine's isocenter using digitally reconstructed radiographs (DRRs) as a reference image set. Both kV and MV images may be used to verify setup.

IGRT Target Localization: In addition to the portal imaging, cone-beam CT (CBCT) images will be acquired prior to treatment for each fraction. By using IGRT to image the plasmacytoma in "real-time", the operator may automatically align the plasmacytoma with the treatment machine on each day of treatment. If shifts are made based upon the CBCT images, the portal images will be repeated.

Treatment Planning: 3D-Conformal or IMRT treatment planning is allowed. This includes "field-in-field" beams as well as the use of dynamic multi-leaf collimator (MLC) derived using inverse

planning or electronic compensator techniques. Field arrangements and technique should be chosen that satisfy the PTV dose coverage constraints and normal tissue dose constraints using Dose-Volume Histogram (DVH) analysis. By carefully selecting the gantry and table angle combinations that do not enter or exit through other organs of the body, the dose can be confined to the traditional treatment volumes.

Non-coplanar beam arrangements are encouraged, but not required.

Dose calculations with tissue inhomogeneity correction must be used.

After completion of the first course of radiotherapy + nivolumab on Day 1 (or within 24 hours of RT), the patient will start on day 15 the regimen of nivolumab 240 mg q2 weeks.

Response assessment will be performed every 2 weeks as standard of care.

6.3 Treatment modifications for Radiation Adverse Events:

Dosing delay: The patient should have resolution or return to pre-treatment baseline of all grade 3-4 toxicities prior to start of the next immunotherapy treatment.

6.4 On Study Evaluations:

As summarized in the [Study Calendar](#), patients are evaluated pre-treatment for measurable disease in the blood and a targetable soft tissue or bony lesion with radiotherapy. Patients will have specified laboratory values measured bi-monthly and evaluated for response as defined by International Myeloma Working Group Criteria. Response assessments will be performed every 2 weeks.

7 Pharmaceutical Information

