7.4 Dose Modifications, Delays or Discontinuation of Nivolumab

Recommendations for OPDIVO modifications are provided in Table 1. There are no recommended dose modifications for hypothyroidism or hyperthyroidism. Interrupt or slow the rate of infusion in patients with mild or moderate infusion reactions. Discontinue OPDIVO in patients with severe or life-threatening infusion reactions.

Table 1: Recommended Dose Modifications for OPDIVO

Adverse Reaction	Severity*	Dose Modification
Colitis	Grade 2 diarrhea or colitis	Withhold dose ^a
	Grade 3 diarrhea or colitis	Withhold dose ^a when administered as a single agent
	Grade 4 diarrhea or colitis	Permanently discontinue when administered with ipilimumab
Pneumonitis	Grade 2 pneumonitis	Withhold dose ^a
	Grade 3 or 4 pneumonitis	Permanently discontinue
Hepatitis/non-HCC ^b	Aspartate aminotransferase (AST) or alanine aminotransferase (ALT) more than 3 and up to 5 times the upper limit of normal (ULN) or total bilirubin more than 1.5 and up to 3 times the ULN	Withhold dose ^a
	AST or ALT more than 5 times the ULN or total bilirubin more than 3 times the ULN	Permanently discontinue
Hepatitis/ HCC ^b	
 If AST/ALT is within normal limits at baseline and increases to more than 3 and up to 5 times the ULN If AST/ALT is more than 1 and up to 3 times ULN at baseline and increases to more than 5 and up to 10 times the ULN If AST/ALT is more than 3 and up to 5 times ULN at baseline and increases to more than 8 and up to 10 times the ULN 	Withhold dose ^a

Table 1: Recommended Dose Modifications for OPDIVO

Adverse Reaction	Severity*	Dose Modification
	If AST or ALT increases to more than 10 times the ULN or total bilirubin increases to more than 3 times the ULN	Permanently discontinue
Hypophysitis	Grade 2 or 3 hypophysitis	Withhold dose ^a
	Grade 4 hypophysitis	Permanently discontinue
Adrenal Insufficiency	Grade 2 adrenal insufficiency	Withhold dose ^a
	Grade 3 or 4 adrenal insufficiency	Permanently discontinue
Type 1 Diabetes Mellitus	Grade 3 hyperglycemia	Withhold dose ^a
	Grade 4 hyperglycemia	Permanently discontinue
Nephritis and Renal Dysfunction	Serum creatinine more than 1.5 and up to 6 times the ULN	Withhold dose ^a
	Serum creatinine more than 6 times the ULN	Permanently discontinue
Skin	Grade 3 rash or suspected Stevens-Johnson syndrome (SJS) or toxic epidermal necrolysis (TEN)	Withhold dose ^a
	Grade 4 rash or confirmed SJS or TEN	Permanently discontinue

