Encephalitis	New-onset moderate or severe neurologic signs or symptoms	Withhold dose ^a
	Immune-mediated encephalitis	Permanently discontinue
Other	Other Grade 3 adverse reaction First occurrence Recurrence of same Grade 3 adverse reactions	Withhold dose ^a Permanently discontinue
	Life-threatening or Grade 4 adverse reaction	Permanently discontinue
	Grade 3 myocarditis	Permanently discontinue
	Requirement for 10 mg per day or greater prednisone or equivalent for more than 12 weeks	Permanently discontinue
	Persistent Grade 2 or 3 adverse reactions lasting 12 weeks or longer	Permanently discontinue

* Toxicity was graded per National Cancer Institute Common Terminology Criteria for Adverse Events, Version 4.0 (NCI CTCAE v4).

^a Resume treatment when adverse reaction improves to Grade 0 or 1.

^b HCC: hepatocellular carcinoma.

^c Resume treatment when AST/ALT returns to baseline.

8 Correlative Studies

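### Section 6.3 and Table 1 of Section 7.4 both control the next nivolumab dose but are not reconciled on delay versus permanent stop, on the restart threshold, or with the dose-limiting-toxicity stop

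*Combined protocol and SAP*

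**What the plan says.** Three parts of the protocol bear on whether a patient with a severe toxicity receives another nivolumab dose.

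- **Section 6.3**, under the heading "Treatment modifications for Radiation Adverse Events", contains only a dosing-delay item: "The patient should have resolution or return to pre-treatment baseline of all grade 3-4 toxicities prior to start of the next immunotherapy treatment". It names no event that ends treatment and does not mention Table 1.
- **Section 7.4** states "Recommendations for OPDIVO modifications are provided in Table 1". Permanent discontinuation is listed against "Life-threatening or Grade 4 adverse reaction", "Grade 3 or 4 pneumonitis", "Grade 3 or 4 adrenal insufficiency", "Grade 3 myocarditis" and recurrence of the same grade 3 reaction. Other grade 3 reactions, including hypophysitis, hyperglycemia, rash and a first occurrence of any other grade 3 reaction, are withheld. The footnote on withheld doses reads "Resume treatment when adverse reaction improves to Grade 0 or 1". Section 7.4 does not mention Section 6.3.
- **Section 5.1.2** continues nivolumab until progression, a time limit or a dose-limiting toxicity (DLT). **Section 11.3.5** counts as DLTs any grade 4 non-hematological toxicity, treatment-related grade 3 non-hematological toxicity, treatment-related death, and any toxicity that interrupts treatment for more than 6 weeks.

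**The concern.** Radiation is five fractions in the first week (Section 5.1.2), so the dose that Section 6.3 delays is a nivolumab dose. Sections 6.3 and 7.4 are therefore two rules for the same drug. One places grade 3 and grade 4 toxicities together under delay. The other makes all grade 4 reactions and several grade 3 reactions permanent stops.

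The section headings suggest a division by cause, but the protocol gives no means of making it. Nivolumab starts with the first fraction. Section 6.1 anticipates chest and abdominal targets. Section 12.1.2 attributes events to study treatment as a whole, and Section 12.2 asks only whether an event is related to the study drug. Pneumonitis after chest irradiation is a foreseeable event that could be placed under either section.

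What is at stake is mainly patient safety. An investigator who consults Section 6.3 alone could treat as a delay an event for which Table 1 ends the drug. Exposure to nivolumab would then depend on which page was consulted.

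**Working it through.** The point rests on no sample size, error rate or event count, so there is nothing to compute. The check is to take each type of event through the three rules.

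| Event | Section 6.3 | Table 1, Section 7.4 | Sections 5.1.2 and 11.3.5 |
|---|---|---|---|
| Grade 4, non-hematological | Delay | Permanent stop | DLT, treatment ends |
| Grade 4, hematological | Delay | Permanent stop (general grade 4 row, not limited by type) | Not a DLT by grade |
| Grade 3 pneumonitis, adrenal insufficiency or myocarditis; recurrent grade 3 reaction | Delay | Permanent stop | DLT if treatment-related and non-hematological |
| First other grade 3 reaction, and grade 3 rash, hypophysitis or hyperglycemia | Delay | Withhold, then resume | DLT if treatment-related and non-hematological |

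1. **Delay versus stop (rows 1 to 3).** Section 6.3 states a condition that must be met before a next dose. Table 1 removes the next dose. Someone who applies both will stop, so there is no strict logical contradiction. But the grade 4 part of Section 6.3 has almost no work to do unless a dose can follow a grade 4 toxicity. Its natural reading is therefore delay, then resume, which Table 1 does not allow.

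2. **Restart threshold (row 4).** Table 1 resumes at grade 0 or 1. Section 6.3 asks for resolution or a return to the pre-treatment level. Exclusion criterion 13 in Section 3.3 bars persistent toxicity of grade 1 or more from prior treatment, so for toxicity of that kind the baseline is grade 0. Take a withheld grade 3 event that has improved to grade 1. Table 1 says resume and Section 6.3 says wait. Reading Section 6.3 as a precondition does not remove this difference.

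3. **The third rule (row 4, last column).** A treatment-related grade 3 rash is a DLT under Section 11.3.5, and under Section 5.1.2 nivolumab continues only until a DLT. Table 1 withholds and then resumes for the same event. The DLT stop therefore does not settle the difference between Section 6.3 and Table 1; it adds another.

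4. **Is there a tie-breaker elsewhere?** Section 5.3 stops treatment for unacceptable adverse events but does not define them. Section 12.3 refers to Section 15 for the definition of unacceptable toxicity, and Section 15 is the stool-collection appendix. No passage says which rule prevails.

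The colitis rows of Table 1 appear broken in the text available and were not used. The hepatitis stop is given as a multiple of the upper limit of normal and not as a grade, so it was left out of the comparison by grade.

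**The case against.** The strongest reply is that nothing in Section 6.3 permits or orders a restart. It is a minimum condition, it is headed for radiation events, and Section 7.4 is by its title the natural place to look for rules on stopping the drug. Table 1 speaks of adverse reactions, which may suggest events caused by nivolumab. Adrenal insufficiency and myocarditis are less obviously events that someone would label as radiation toxicity. The DLT stop would also catch the leading example: grade 3 or 4 pneumonitis attributed to study treatment is a DLT whichever component caused it.

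Much of this stands. A reader might infer that the same patient is told both to restart and to stop. The documents do not support that, because no text instructs re-dosing. Four further inferences also fail:

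- *Grade 2 events.* Section 6.3 is silent on grade 2, so Table 1 applies unopposed. That is not a conflict.
- *Different practice between sites.* Section 11 describes a single-center trial. Any divergence would be between investigators.
- *Distortion of the DLT count through the 6-week interruption criterion.* Treatment-related grade 3 and all grade 4 non-hematological events are DLTs by grade already, so this argument largely fails.
- *A number of patients affected.* The documents give no expected rate of severe toxicity, and none for the narrower group of events that could fall under both sections.

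The reply does not dispose of the rest. Section 6.3 says all grade 3-4 toxicities without limiting them by cause, Table 1's rows are not expressly limited by cause either, and neither section yields to the other. The DLT stop does not reach grade 4 hematological reactions by grade. On the restart threshold Section 6.3 is the stricter text, which weakens any claim that it always leads to premature re-dosing but confirms that the two sections differ.

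**Conclusion.** The concern holds as a safety-relevant inconsistency. For every grade 4 reaction and four grade 3 situations (pneumonitis, adrenal insufficiency, myocarditis, recurrence of the same reaction), Section 6.3 mentions only delay where Table 1 ends nivolumab. For withheld grade 3 reactions the two sections give different restart thresholds. For treatment-related grade 3 non-hematological events, the DLT stop does not match Table 1's withhold-and-resume rows.

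The conclusion on delay versus stop assumes that Section 6.3 may be consulted without Table 1; an investigator who applies both would stop the drug. The conclusion on the threshold assumes a patient whose baseline for the toxicity in question is grade 0. The conclusion on the DLT stop uses the definition in Section 11.3.5 as the meaning of the term in Section 5.1.2, which defines no other. Following the plan as written does not resolve these differences. The size is given as categories of event because the documents support no patient count.

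**What to change.** Amend the protocol so that Section 6.3, Table 1 in Section 7.4, and the DLT stop in Sections 5.1.2 and 11.3.5 agree. The amendment should:

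- state which events Section 6.3 is meant to cover, and cross-reference Table 1;
- state which rule governs nivolumab when an event falls under more than one of these rules or could be due to either treatment;
- use a single restart threshold wherever restart is mentioned;
- say whether reaching a DLT ends treatment for the grade 3 events that Table 1 withholds and resumes.

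The Section 12.3 reference to Section 15 for unacceptable toxicity should be corrected at the same time. Which clinical rule applies is for the sponsor-investigator and the drug supplier to decide; no view on that is offered here. The cost is one or two sentences for the core of the change plus the cross-references, with no added patients, visits or procedures and no effect on the sample size.
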